5.6. Study Drug Accountability

The investigator or designee (eg, pharmacist) is responsible for ensuring adequate accountability of all used and unused study drug. This includes acknowledgement of receipt of each shipment of study drug (quantity and condition), subject administration and dispensing records, and returned or destroyed study product. Administration and dispensing records will document quantities received from Gilead Sciences and quantities administered/dispensed to subjects, including the lot number, date administered/dispensed, subject identification number, subject initials, and the initials of the person dispensing the medication. All used and unused study drug administered/dispensed to subjects must be returned to the site.

Investigational Drug Accountability records will be provided to each study site to:

- Record the date and quantity of study drug received
- Record the date, subject number, subject initials, and the study drug assigned
- Record the date, quantity of used and unused study drug. Dispensing records will include the initials of the person recording the information.

5.6.1. Investigational Medicinal Product Return or Disposal

At the start of the study, the study monitor will evaluate each study center's study drug disposal procedures and provide appropriate instruction for return or destruction of unused study drug supplies. If the site has an appropriate Standard Operating Procedure (SOP) for drug destruction, the site may destroy used (empty bottles) and unused study drug supplies performed in accordance with the site's (hospital/pharmacy) SOP. If the site does not have acceptable procedures in place for drug destruction, arrangements will be made between the site and Gilead Sciences (or Gilead Sciences' representative) for return of unused study drug supplies. A copy of the site's SOP will be obtained for central files. Where possible, study drug will be destroyed at the site. Upon study completion, a copy of the Investigational Drug Accountability records must be filed at the site. Another copy will be returned to Gilead Sciences. If drug is destroyed. Records must show the identification and quantity of each unit destroyed, the method of destruction, and person who disposed of the drug. All study drug records must be maintained at the site and copies must be submitted to Gilead Sciences at the end of the study.

6. **STUDY PROCEDURES**

The study procedures to be conducted for each subject enrolled in the study are presented in tabular form in Appendix 2 and described in the text that follows.

The site must document any deviation from protocol procedures and notify the sponsor or contract research organization (CRO).

6.1. Subject Enrollment and Treatment Assignment

It is the responsibility of the investigator to ensure that subjects are eligible to participate in the study prior to enrollment and throughout the study.

Documentation of the personally signed and dated informed consent of each subject, using the study-specific ICF, is required before initiating the Screening process. In subjects with HE, which may impair decision-making, consent will be obtained per hospital procedures (eg, by Legally Authorized Representative).

After written informed consent has been obtained and eligibility to participate established, investigative site personnel will obtain the subject's identification number and study drug assignment from the IWRS.

6.2. Pretreatment Assessments

6.2.1. Screening Visit

Local laboratory results obtained within one day of Screening may be used to determine eligibility.

Chest x-rays, local laboratory testing for Hepatitis B and C and HIV Serology, and urine drug testing done during the current hospitalization (which includes transfers from other institutions) and within 10 days of Screening may be used to determine eligibility. A urine pregnancy test must be done locally on the day of the Screening visit.

NOTE: All subjects will require an additional set of Screening labs drawn for central lab processing.

Subjects will be screened within 14 days prior to randomization to determine eligibility for participation in the study.

The interval between hospitalization and Baseline/Day 1 must be ≤ 14 days. This window may be extended under special circumstances with explicit approval from the Medical Monitor.

Subjects who fail to meet eligibility criteria due to an abnormal laboratory result may undergo re-testing of the abnormal analyte once during the Screening window.

Upon pre-approval by the Medical Monitor, subjects who fail to meet eligibility criteria may be re-screened once if there is a reasonable expectation that the subject will meet eligibility after repeat screening.

Day -14 to Day 0

The following will be performed and documented at Screening:

- Obtain written informed consent
- PPD
- Obtain medical history
- Review and record whether the subject has met inclusion/exclusion criteria
- AUDIT / SADQ questionnaire
- Assess alcohol consumption
- Complete PE including, vital signs, body weight, and height
- Record all concomitant medications that the subject has taken within 30 days prior to Screening
- Perform standard 12-lead ECG
- The following laboratory tests will be collected and performed at **both** the local and central laboratories:
 - Urine sample for drug screen
 - Hematology
 - Chemistry: ALT, AST, albumin, alkaline phosphatase, bicarbonate, blood urea nitrogen (BUN), calcium, chloride, creatinine, glucose, lactate dehydrogenase (LDH), magnesium, phosphorus, potassium, sodium, total and direct bilirubin, total protein, uric acid, gamma-glutamyl transferase (GGT)
 - Coagulation Tests: PT, PTT, and INR
 - HBsAg
 - Anti-HCV with HCV RNA reflex if positive antibody
 - HIV antibody

Note: Eligibility will be based on local laboratory results.

However, subjects whose HIV or hepatitis B or C serologies from the central laboratory are positive must stop study drug within 3 days of receipt of results. All subjects stopping study drug for these reasons should attend an EoT visit as soon as possible and have a follow up visit 30 days after their last dose of study drug, prior to being withdrawn from the study.

The following tests will be performed by the local laboratory **only**:

- Urine samples for urinalysis (routine and microscopic) and culture
- Urine Pregnancy Test (only for female subjects of childbearing potential)
- Blood cultures

Note: Subjects may be eligible based on their local urine pregnancy test; however, if the subject has a positive serum pregnancy test from central laboratory testing (see below), the subject must stop study drug immediately upon receipt of the central laboratory result, attend an EoT visit as soon as possible, and have a follow-up visit 30 days after their last dose of study drug, prior to being withdrawn from the study.

- Obtain blood samples for the following to be sent to the central laboratory **only**:
 - Blood for Biomarkers
 - Insulin
 - Lipid Profile
 - Serum Pregnancy Test (only for females subjects of childbearing potential)
- Assessments for HE, ascites, Hepatorenal Syndrome (HRS), and infection
- Perform chest x-ray (posteroanterior [PA] film is mandatory and a lateral film should be performed if feasible). Chest x-rays performed during the current hospitalization (which includes transfers from other institutions) and within 10 days of Screening are acceptable.
- Perform liver ultrasound (it is acceptable to use a liver ultrasound previously performed during the current hospitalization, including transfers between hospitals.)
- Perform paracentesis (ascitic fluid tap) with ascitic fluid cell count, differential, and culture if clinically-detectable ascites is present (laboratory specimens to be analyzed by the local laboratory only)

• Perform liver biopsy

Note: Can be performed up to 7 days post Baseline/Day 1. Liver biopsy obtained during the current hospitalization (including transfers between hospitals) prior to Screening is acceptable. However, if biopsy results are not consistent with AH, the subject will stop study drug within 3 days of receipt of the liver biopsy result, attend an EoT visit as soon as possible, and have a follow-up visit 30 days after their last dose of study drug, prior to being withdrawn from the study. If the liver biopsy sample is inadequate to confirm a pathologic diagnosis of AH and no alternative diagnosis is suggested on biopsy, then the subject may remain in the study.

• Record any serious adverse events (SAEs) and all adverse events related to protocol-mandated procedures occurring after signing of the consent form

From the time of obtaining informed consent through the first administration of investigational medicinal product, record all SAEs, as well as any adverse events related to protocol-mandated procedures on the adverse events case report form (eCRF). All other untoward medical occurrences observed during the Screening period, including exacerbation or changes in medical history are to be captured on the medical history eCRF. See Section 7 Adverse Events and Toxicity Management for additional details.

Subjects must meet all of the inclusion criteria and none of the exclusion criteria prior to randomization into the study.

6.2.2. Baseline / Day 1 Assessments and Randomization

After review of inclusion and exclusion criteria to confirm eligibility, subjects will be randomized to study drug assignment and receive their Subject Identification Number via the IWRS prior to their first dose of study drug.

Randomization will be stratified by MELD < or ≥ 25 at Screening as calculated using local laboratory tests and an online MELD calculator (see Section 6.9.7).

During the entire hospitalization period, subjects will be evaluated daily with assessments to include a review of adverse events, concomitant medications, study drug adherence, and a symptom-directed PE including assessments for ascites and HE. Findings based on these assessments and laboratory investigations obtained by treating physicians as part of routine care will be assessed by the investigator for triggers that may necessitate further evaluation and/or treatment discontinuation and managed accordingly per Section 7.5 of the protocol.

The following will be performed and documented at the randomization visit prior to dosing:

- Review inclusion/exclusion criteria and confirm eligibility
- QoL Questionnaire (CLDQ)

- Assess alcohol consumption
- Complete PE including vital signs and body weight
- Perform standard 12-lead ECG
- Assessments for HE, ascites, HRS, and infection
- Obtain blood samples for:
 - Hematology
 - Chemistry: ALT, AST, albumin, alkaline phosphatase, bicarbonate, BUN, calcium, chloride, creatinine, glucose, LDH, magnesium, phosphorus, potassium, sodium, total and direct bilirubin, total protein, uric acid, GGT. Samples should be drawn for central and local laboratory testing for the calculation of the Lille Score (Section 6.9.12)
 - Coagulation Tests: PT, PTT, and INR. Samples should be drawn for central and local laboratory testing for calculation of the Lille Score (Section 6.9.12)
 - Blood and Urine for Biomarkers
 - ELF^{TM} Test and LOXL2
 - Insulin
 - Hemoglobin A1c
 - Lipid Profile
 - Sparse PK Sample (collected after dosing)
 - ___ PPD
- Urine pregnancy test (for females of childbearing potential)
- Collect stool for microbiome testing
- Record all concomitant medications that the subject has taken since the previous visit
- Record any SAEs and all adverse events occurring after signing of the consent form
- Randomization via IWRS (Note: stratification assignment is based on MELD score as calculated using local laboratory results and an online MELD calculator (see Section 6.9.7).

- Administer or dispense GS-4997/placebo and prednisolone, and provide subject with dosing instruction on appropriate dosing and administration
- FibroScan (if available and for subjects without ascites).
- 6.3. Treatment Assessments

6.3.1. Week 1 Visit (±3 Days)

During the Week 1 safety visit the following will be performed and documented:

- Review of liver biopsy and central laboratory results if unavailable during the Screening or baseline period and reassess study entry criteria.
- Assess alcohol consumption
- Complete PE including, vital signs
- Assessments for HE, ascites, HRS, and infection
- Obtain blood samples for:
 - Hematology
 - Chemistry: ALT, AST, albumin, alkaline phosphatase, bicarbonate, BUN, calcium, chloride, creatinine, glucose, LDH, magnesium, phosphorus, potassium, sodium, total and direct bilirubin, total protein, uric acid, GGT. Samples should be drawn for central and local laboratory testing for calculation of the Lille Score (Section 6.9.12)
 - Coagulation Tests: PT, PTT, and INR.
 - Blood for Biomarkers
 - Sparse PK Sample
- Record all concomitant medications that the subject has taken since the previous visit
- Record any SAEs and all adverse events occurring since the previous visit
- Administer or dispense prednisolone, and provide subject with dosing instruction on appropriate dosing and administration.
- PPD
- Assess for study drug adherence

- Perform study drug accountability
- Calculate Lille Score at Week 1 based on local laboratory results (Section 6.9.12). If Lille score is ≥ 0.56 (null response), prednisolone treatment should be held. If Lille score is > 0.85, then both study drugs should be held. If the central lab results confirm Lille score stopping criteria has been met, the subject will be prematurely discontinued from study drug(s), as appropriate.

6.3.2. Week 2 Visit (±3 Days)

During the Week 2 safety visit, the following will be performed and documented:

- Assess alcohol consumption
- Complete PE including vital signs
- Assessments for HE, ascites, HRS and infection
- Obtain blood samples for:
 - Hematology
 - Chemistry: ALT, AST, albumin, alkaline phosphatase, bicarbonate, BUN, calcium, chloride, creatinine, glucose, LDH, magnesium, phosphorus, potassium, sodium, total and direct bilirubin, total protein, uric acid, GGT. Samples should be drawn for central and local laboratory testing for the calculation of the Lille Score (Section 6.9.12)
 - Coagulation Tests: PT, PTT, and INR
 - Blood for Biomarkers
 - Sparse PK Sample
- Record all concomitant medications that the subject has taken since the previous visit
- Record any serious adverse events and all adverse events occurring since the previous visit
- PPD
- Assess for Study Drug adherence
- Perform study drug accountability
- Calculate Lille Score at Week 2 based on local laboratory results (Section 6.9.12). If Lille score is > 0.85, then both study drugs should be held. If the central lab results confirm Lille

score stopping criteria have been met, the subject will be prematurely discontinued from study drug(s), as appropriate.

6.3.3. Week 3 Visit (±3 Days)

During the Week 3 safety visit, the following will be performed and documented:

- Assess alcohol consumption
- Complete PE including vital signs
- Assessments for HE, ascites, HRS and infection
- Obtain blood samples for:
 - Hematology
 - Chemistry: ALT, AST, albumin, alkaline phosphatase, bicarbonate, BUN, calcium, chloride, creatinine, glucose, LDH, magnesium, phosphorus, potassium, sodium, total and direct bilirubin, total protein, uric acid, GGT. Samples should be drawn for central and local laboratory testing for the calculation of the Lille Score (Section 6.9.12)

- Coagulation Tests: PT, PTT, and INR

- Record all concomitant medications that the subject has taken since the previous visit
- Record any SAEs and all adverse events occurring since the previous visit
- Administer or dispense prednisolone, and provide subject with dosing instruction on appropriate dosing and administration
- PPD
- Assess for study drug adherence
- Perform study drug accountability
- Calculate Lille Score at Week 3 based on local laboratory results (Section 6.9.12). If Lille score is > 0.85, then both study drugs should be held. If the central lab results confirm Lille score stopping criteria have been met, the subject will be prematurely discontinued from study drug(s), as appropriate.

6.3.4. Week 4 / End of Treatment Visit (EoT) (±3 days)

If the subject meets criteria for discontinuation of treatment (see Section 6.8 of this protocol), the subject should complete an EoT visit as soon as possible after all study drugs are discontinued and attend post-treatment visits as outlined in Appendix 2. Subjects discontinued prior to Week 2 should attend a 30-day FU visit to collect safety data within 30 days of their last dose of study drug. Subjects that have their scheduled Week 4/End of Treatment visit prior to Day 28 will require a phone contact between Study Days 28-35 to assess mortality and liver transplantation.

Subjects should be instructed not to take study drug in the morning of the Week 4 Visit. The dose should be taken as soon as possible after the trough PK (Sparse PK sample collected prior to dosing) and biomarker assessments are completed.

The following will be performed and documented at this visit:

- QoL Questionnaire (CLDQ)
- Assess alcohol consumption
- Complete PE including, vital signs, and body weight
- Perform standard 12-lead ECG
- Assessments for HE, ascites, HRS, and infection.
- Obtain blood samples for:
 - Hematology
 - Chemistry: ALT, AST, albumin, alkaline phosphatase, bicarbonate, BUN, calcium, chloride, creatinine, glucose, LDH, magnesium, phosphorus, potassium, sodium, total and direct bilirubin, total protein, uric acid, GGT. Samples should be drawn for central and local laboratory testing for the calculation of the Lille Score (Section 6.9.12)
 - Coagulation Tests: PT, PTT, and INR
 - Blood and Urine for Biomarkers
 - ELF^{TM} Test and LOXL2
 - Insulin
 - Lipid Profile
 - Sparse PK Sample

- Urine pregnancy test (for females of childbearing potential)
- Collect stool for microbiome testing
- Record all concomitant medications that the subject has taken since the previous visit
- Record any SAEs and all adverse events occurring since the previous visit
- Assess for study drug adherence
- Perform study drug accountability
- FibroScan (if available and for subjects without ascites)
- Record local laboratory results for total bilirubin so that Lille score can be calculated using local laboratory data.

6.3.5. Follow Up Visit (±5 Days)

Subjects should return for a Follow-Up Visit 30 days after their last dose of study drug.

Subjects whose liver biopsy results are not consistent with AH or whose HIV or hepatitis B or C serologies from the central laboratory are positive, must stop study drug within 3 days of receipt of results. If the liver biopsy sample is inadequate for pathologic diagnosis of AH and no alternative diagnosis is suggested on biopsy, then the subject may remain in the study. Subjects whose serum pregnancy testing from the central laboratory is positive at Screening must stop study drug immediately upon receipt of this result. All subjects stopping study drug for these reasons should attend an EoT visit as soon as possible and have a follow up visit 30 days after their last dose of study drug, prior to being withdrawn from the study. Subjects discontinuing both study drugs prior to Week 2 should complete an end of treatment visit after stopping drug, a 30-day safety FU visit, and all post-treatment follow-up visits. Subjects discontinued after Week 2 should complete an end of treatment assessments as outlined in Appendix 2.

- Record all concomitant medications that the subject has taken since the previous visit
- Record any SAEs and all adverse events occurring since the previous visit
- Assessments for HE, ascites, HRS and infection

- Obtain blood samples for:
 - Hematology
 - Chemistry: ALT, AST, albumin, alkaline phosphatase, bicarbonate, BUN, calcium, chloride, creatinine, glucose, LDH, magnesium, phosphorus, potassium, sodium, total and direct bilirubin, total protein, uric acid, GGT

- Coagulation Tests: PT, PTT, and INR

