6.4.2. Intensive PK Substudy

6.5. Post-Treatment Assessments

6.5.1. Week 6 (± 3 Days)

Subjects will return for Follow-Up Visits starting at Week 6 after the Week 4 / EoT Visit or the last dose of study drug to undergo the following:

- Assess alcohol consumption
- Complete PE including vital signs
- Assessments for HE, ascites, HRS and infection
- Obtain blood samples for:
 - Hematology
 - Chemistry: ALT, AST, albumin, alkaline phosphatase, bicarbonate, BUN, calcium, chloride, creatinine, glucose, LDH, magnesium, phosphorus, potassium, sodium, total and direct bilirubin, total protein, uric acid, GGT
 - Coagulation Tests: PT, PTT, and INR

- Record all concomitant medications that the subject has taken since the previous visit
- Record any serious adverse events and all adverse events occurring since the previous visit

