6.5.2. Weeks 8, 16, and 20 / Post Treatment Visits (± 5 Days)

During the Week 8, 16, and 20 post treatment visits, the following will be performed and documented:

- Assess alcohol consumption
- Complete PE including, vital signs
- Perform standard 12-lead ECG (Week 8 only)
- Assessments for HE, ascites, HRS and infection
- Obtain blood samples for:
 - Hematology
 - Chemistry: ALT, AST, albumin, alkaline phosphatase, bicarbonate, BUN, calcium, chloride, creatinine, glucose, LDH, magnesium, phosphorus, potassium, sodium, total and direct bilirubin, total protein, uric acid, GGT
 - Coagulation Tests: PT, PTT, and INR
 - Blood for Biomarkers (Week 8 only)
- Urine pregnancy test (for females of childbearing potential)
- Record all concomitant medications that the subject has taken since the previous visit
- Record any serious adverse events and all adverse events occurring since the previous visit (Week 8 only)
- Record procedure-related adverse events and procedure-related SAEs as well as any SAEs that the investigator deems relevant to the use of study drug for Weeks 16 and 20 only
- Subjects that have their scheduled Week 8 visit prior to Day 56 will require a phone contact between Day 56-63 respectively, to assess for mortality and liver transplantation.

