6.7. Assessments for Premature Discontinuation from Study

Discontinuation from study drug dosing and discontinuation from the study (including follow-up visits and phone contact at Week 8, Week 12, and Week 24) are 2 distinct actions.

Subjects with histologically confirmed AH who discontinue study drug (for any reason other than death) prior to completion of the assigned dosing period, should complete an EoT visit, a 30 day follow up visit, and all required follow-up study visits.

Subjects whose liver biopsy results are not consistent with AH or whose HIV or hepatitis B or C serologies from the central laboratory are positive, must stop study drug within 3 days of receipt of results. Subjects whose serum pregnancy testing from the central laboratory is positive at Screening must stop study drug immediately upon receipt of this result. All subjects stopping study drug for these reasons should attend an EoT visit as soon as possible and have a follow up visit 30 days after their last dose of study drug, prior to being withdrawn from the study. These subjects will not complete the remaining follow-up study visits.

Subjects are considered to have completed the study after the Follow up Week 24 visit, regardless of treatment duration and/or early termination from study drug.

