6.9.12. Lille Score

The Lille score should be calculated at Day 7 using local laboratory results from Baseline/Day 1 (albumin, total bilirubin, creatinine, PT) and Week 1 (total bilirubin) for all subjects utilizing the following calculator (http://www.mdcalc.com/lille-model-alcoholic-hepatitis/), in appropriate units (SI or conventional).

Prednisolone should be discontinued in subjects with a Lille Score ≥ 0.56 at Day 7 (null response); these subjects may continue GS-4997/placebo treatment.

For safety monitoring of the stopping criteria of Lille score > 0.85, sites should also collect local laboratory results for total bilirubin at Weeks 2, 3, and 4 and use the same calculator to calculate the Lille Score compared to baseline values. When performing the calculation, ensure the Day 7 total bilirubin is changed to Week 2, 3, and 4 values at the appropriate time points.

If a subject's Lille score is > 0.85 at any time, they should stop both study drugs. If the central laboratory Lille score calculation is different from the local laboratory results, the stopping criteria will be based on central laboratory results.

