Preclinical data indicate that GS-4997 is unlikely to reduce the exposure of hormonal contraceptives through induction of human drug metabolizing enzymes or drug transporters. This is supported by clinical DDI data, which demonstrated multiple doses of GS-4997 did not result in increased activity of CYP3A4 or P-gp based on plasma exposures of sensitive probe substrates (midazolam and digoxin). Similarly, preclinical and clinical data indicate GS-4997 is unlikely to cause a clinically relevant increase in the exposure of hormonal contraceptives through inhibition of drug metabolizing enzymes or drug transporters. Please refer to the latest version of the investigator's brochure for additional information.

b. Contraception Requirements for Female Subjects of Childbearing Potential

The inclusion of female subjects of childbearing potential requires the use of highly effective contraceptive measures. They must have a negative serum pregnancy test at Screening and a negative pregnancy test on the Baseline/Day 1 visit prior to randomization. Pregnancy tests will be performed at monthly intervals thereafter. Female subjects must agree to one of the following from Screening until 90 days after the last dose of study drug.

• Complete abstinence from intercourse of reproductive potential. Abstinence is an acceptable method of contraception only when it is in line with the subject's preferred and usual lifestyle.

Or

- Consistent and correct use of 1 of the following methods of birth control listed below.
 - Intrauterine device (IUD) with a failure rate of < 1% per year
 - Tubal sterilization
 - Essure micro-insert system (provided confirmation of success 3 months after procedure)
 - Vasectomy in the male partner (provided that the partner is the sole sexual partner and had confirmation of surgical success 3 months after procedure)
- The above described methods are considered preferred methods of highly effective contraception in this protocol.
 - Should female subjects wish to use a hormonally based method, use of a male condom by the female subject's male partner is required. Subjects who utilize a hormonal contraceptive as one of their birth control methods must have used the same method for at least three months prior to study dosing. Hormonally-based contraceptives permitted for use in this protocol are as follows:
 - Hormonal methods (each method *must* be used with a condom in the male partner)
 - Oral contraceptives (either combined or progesterone only)

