The screening and randomization phase will take approximately 2 weeks; and study drugs will be administered for a total of 28 days. Subjects will be followed for a total of 24 weeks (ie, 20 weeks following last dose of study drug); with the exception of subjects who have a biopsy that is consistent with an alternative etiology for liver disease; and those with positive serologies for HBsAg, HIV, or hepatitis C virus (HCV)-these subjects will be followed to last dose date plus 30 days for safety evaluation. Laboratory results (serum chemistry, hematology, coagulation tests), calculation of MELD, CPT (includes clinical assessments of hepatic encephalopathy and ascites) and Maddrey DF scores, and collection of vital signs, alcohol consumption, and concomitant medications and assessment of HRS and infections will be performed at screening, Day 1, Weeks 1, 2, 3, 4, 6 and 8 and every 4 weeks thereafter through Week 24. Lille score will be calculated at Weeks 1, 2, 3, and 4. Adverse events will be collected through the last dose date of any study drug plus 30 days. Serious adverse events (SAEs) not related to study endpoints will be collected up to last dose date + 30 days. Adverse events and SAEs related to study endpoints (eg, deaths, infections, and HRS) will be collected throughout the study. Insulin, lipid profiles, and weight will be collected at screening, baseline, and at Weeks 4, 12, and 24. HbA1c will follow the lipid schedule, but will not be collected at screening or Week 4. Investigator assessment of 12-lead electrocardiograms (ECG) will be collected at screening, baseline and at Weeks 4 and 8. Pregnancy testing for women of childbearing potential will be performed at screening (serum), Day 1, and every 4 weeks throughout the study.

ELF score will be collected at baseline, and at Weeks 4, 12 and 24; and the Alcohol Use Disorders Identification Test (AUDIT) and Severity of Alcohol Dependence Questionnaire (SADQ) will be administered at screening to determine levels of alcohol use and dependence on alcohol.

Single PK samples will be collected on Day 1 and at Weeks 1, 2, and 4. Subjects participating in the PK substudy will have a full profile collected between Weeks 1 and 3 of the study.

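### Women who stop both drugs in Week 1 and stay in the study have no scheduled pregnancy test for about 41-59 days, although the protocol promises monthly tests

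*Protocol*

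**What the plan says.** Two places state how often women of childbearing potential are tested. Protocol Appendix 3, item 2b, requires negative tests at Screening and Baseline/Day 1 and adds: "Pregnancy tests will be performed at monthly intervals thereafter". SAP 1.2 says that testing "will be performed at screening (serum), Day 1, and every 4 weeks throughout the study".

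The visit lists carry the test at Baseline/Day 1 (6.2.2), Week 4/EoT (6.3.4), Weeks 8, 16 and 20 (6.5.2) and Weeks 12 and 24 (6.5.3). They carry none at Week 6 (6.5.1), at the 30-day Follow-Up visit (6.3.5) or at unscheduled visits (6.6). In Appendix 2 the pregnancy row is blank in those same three columns, so text and table agree.

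For early stoppers, 6.3.5 sets the visits: "Subjects discontinuing both study drugs prior to Week 2 should complete an end of treatment visit after stopping drug, a 30-day safety FU visit", and then the post-treatment visits. A subject with a Lille score above 0.85 is one example of an early stopper: under 6.9.12 "they should stop both study drugs". Section 6.7 says that subjects with confirmed disease who stop early "should complete an EoT visit, a 30 day follow up visit, and all required follow-up study visits". Appendix 2, footnote t, has early stoppers complete the Week 4/EoT procedures when they stop. They also get a telephone call in Days 28-35 about death and transplantation. Section 6.3.4 uses the same call for a Week 4/EoT visit held before Day 28: such subjects "will require a phone contact between Study Days 28-35 to assess mortality and liver transplantation". Women withdrawn for a biopsy not consistent with alcoholic hepatitis, or for positive serology, attend EoT and the 30-day Follow-Up visit and then leave (6.7).

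**The concern.** The stated interval works only for subjects who follow the normal calendar. When both drugs stop early, the test that belongs to Week 4 moves forward to EoT, and nothing takes its place until Week 8. The one in-person safety visit designed for early stoppers, 30 days after the last dose, draws blood for haematology, chemistry and coagulation but does not include a pregnancy test.

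Appendix 3 treats GS-4997 as contraindicated in pregnancy because animal data raise a suspicion of malformations, and it requires contraception for 90 days after the last dose. What is at stake is timely detection of an exposed pregnancy. For withdrawn women, anything after EoT depends on the woman telling the investigator (Appendix 3, item 5) and on the investigator reporting it (7.6.2.1).

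**Working it through.** **Inputs.** Week 4 is Day 28 ±3, so Days 25-31. Week 8 is Day 56 ±5, so Days 51-61; 6.5.2 ties Week 8 to Day 56, so visits count from Day 1. Week 12 is Day 84 ±5, so Days 79-89. Follow-Up is last dose + 30 ±5 days (6.3.5). EoT after an early stop has no day count in the protocol; I assume 1-3 days after the last dose.

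**Method.** The shortest gap is the earliest next test minus the latest previous test. The longest gap is the latest next test minus the earliest previous test.

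**The plan's own interval, for completers.** Day 1 to nominal Week 4 is 28 − 1 = 27 days, and Week 4 to Week 8 is 56 − 28 = 28 days. The stated frequency is reproduced. With windows:

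- Day 1 to Week 4: 25 − 1 = 24 to 31 − 1 = 30 days
- Week 4 to Week 8: 51 − 31 = 20 to 61 − 25 = 36 days
- Week 8 to Week 12: 79 − 61 = 18 to 89 − 51 = 38 days

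The fair comparator is therefore 38 days, the most that the windows allow a completer.

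**Early stoppers who stay in the study.** After EoT come the telephone call, the Follow-Up visit and Week 6 ("Subjects will return for Follow-Up Visits starting at Week 6"). None has a test, so the next one is at Week 8.

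| Last dose | EoT | Gap to Week 8 |
|---|---|---|
| Day 1 | Day 2-4 | 51 − 4 = 47 to 61 − 2 = 59 days |
| Day 7 | Day 8-10 | 51 − 10 = 41 to 61 − 8 = 53 days |
| Day 14 | Day 15-17 | 51 − 17 = 34 to 61 − 15 = 46 days |
| Day 21 | Day 22-24 | 51 − 24 = 27 to 61 − 22 = 39 days |

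For Week 1 stops as a whole the gap is 41-59 days. At nominal Week 8 the gap exceeds 38 days when 56 − (last dose + lag) > 38, that is, when last dose + lag is at most 17. This means last doses up to Day 16, 15 or 14 for a lag of 1, 2 or 3 days.

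**Sensitivity to the lag.** If EoT came 7 days after a Day 7 last dose, on Day 14, the gap would be 51 − 14 = 37 to 61 − 14 = 47 days.

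**With a test at Follow-Up.** EoT to Follow-Up is 25 − 3 = 22 to 35 − 1 = 34 days. Follow-Up to Week 8 after a Day 7 last dose (Follow-Up on Day 32-42) is 51 − 42 = 9 to 61 − 32 = 29 days. After a Day 1 last dose (Follow-Up on Day 26-36) it is 51 − 36 = 15 to 61 − 26 = 35 days. The longest gap for Week 1 stops is then 35 days.

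**Withdrawn women.** Their last in-person contact is 25-35 days after the last dose and has no test. Counted from Day 1, a 4-week test falls due about Day 29, and after a Day 7 last dose Follow-Up is on Day 32-42. Counted from EoT, a 4-week test falls due 29-31 days after the last dose, which may come before or after Follow-Up.

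**Numbers affected.** The documents do not give them. If 5-15% of 100 subjects stop both drugs this early and 20-30% of those are women of childbearing potential (both assumptions), that is 100 × 0.05 × 0.20 = 1 to 100 × 0.15 × 0.30 = 4.5 women. Section 4.1 allows up to 20 extra subjects for unconfirmed disease; at 20-30% that is 4-6 women. SAP 4.2.2 reports no positive central serology, so in practice the withdrawn group is the biopsy group.

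**The case against.** The strongest reply is that the requirement already exists. Appendix 3 asks for monthly tests and exempts nobody, and 6.6 lets the investigator add assessments. On that view the procedure list is incomplete but the rule is in place. This stands as a description, but sites work from the visit table, and no scheduled contact between EoT and Week 8 tells them to test.

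The size can also be disputed. The 1-3 day lag is an assumption. Under 6.3.1 a high Lille score first leads to the drugs being held, and permanent discontinuation follows central-laboratory confirmation, so EoT may come later and the gap shrink. The sensitivity figure of 37-47 days allows for this. A reader might also count every gap above 31 days as a breach, which would bring in stops up to about Day 21-23. The documents do not support that, because the windows already give completers up to 38 days.

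For withdrawn women, a reader might infer that a monthly test is missed. Neither document says whether the interval runs from Day 1 or from the last test, so no clear breach can be shown. Nor do the documents give a detection lag from which to say that a prompt EoT test would miss conceptions during exposure. What remains is that a later exit test would be better timed.

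Finally, dosing has ended, so the missing test cannot prevent exposure. Contraception, the earlier negative tests and the in-person Follow-Up visit all lower the risk. That is correct and keeps the point small.

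**Conclusion.** The schedule does not deliver the stated interval for women of childbearing potential who stop both drugs early and remain in the study. After a Week 1 stop the gap is 41-59 days on the assumed 1-3 day EoT lag, against at most 38 days for completers. The excess at nominal visits disappears for last doses after about Day 14-16. Under 6.3.5 and 6.7 testing resumes at Week 8, so this is a delay.

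One conflict matters here. Appendix 2, footnote t, says that early stoppers for any reason have the Follow-Up visit before they are withdrawn. Sections 3.2, 6.3.5 and 6.7 keep those with confirmed disease in follow-up. If a site followed the footnote, EoT would be the last test for these women too.

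For women withdrawn after biopsy the point is secondary: their final visit is a sensible place for a test. A reader might infer that the safety results are compromised. They are not: no efficacy or safety estimate, analysis set or stopping rule changes. This is a cheap improvement in safety ascertainment for a few women.

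**What to change.** Add a local urine pregnancy test, for women of childbearing potential who stopped study drug early, to the list in 6.3.5 and as a footnoted entry in the Follow Up column of Appendix 2. Align footnote t with 6.3.5 and 6.7 at the same time. Completers need nothing new: with a last dose on Day 28 their Follow-Up visit falls on Day 53-63, beside the Week 8 test on Day 51-61. SAP Listing 16.2.8.1.5.3 already presents urine pregnancy results for the Safety Analysis Set and needs no change.

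The cost is one line, one table cell and one dipstick at an existing visit. The fix is partial: withdrawn women would still rely on self-report for the last 90 − 35 = 55 to 90 − 25 = 65 days of the contraception window.
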